Current research remains inconclusive regarding the indications for internal mammary radiation therapy (IMRT). Intraoperative IMR lymph node biopsy studies indicate that the positive rate of internal mammary lymph nodes varies between 10% to 40% depending on the tumor's quadrant, while the recurrence rate after systemic treatment is less than 5%. Recent prospective multicenter postoperative adjuvant radiotherapy studies have incorporated the internal mammary field into treatment targets, demonstrating local control and long-term survival benefits. Guidelines recommend IMR irradiation for patients with high preoperative imaging-predicted internal mammary lymph node metastasis risk, primary tumors in the medial quadrant or central region with axillary lymph node metastasis, or other high-risk internal mammary lymph node metastasis probabilities. Notably, for patients with tumors in the internal quadrant or central region and N2 status, the internal mammary lymph node metastasis rate can exceed 40%. This study aims to perform intraluminal radiotherapy in the inner quadrant/central region under full informed consent of patients.

Currently, there are no definitive biomarkers in clinical practice to predict whether breast cancer patients will benefit from radiotherapy. In translational research, NART can directly evaluate the effectiveness of radiotherapy for breast tumors, identify predictors and biomarkers of radiation response, advance radiobiological studies of tumors and normal tissues, and guide personalized treatment plans for breast cancer patients. A secondary objective of the PAPBI13 trial was to explore gene expression profiles that predict radio-sensitivity. Significant changes in gene expression were observed in specimens before and after radiotherapy, primarily involving p53 signaling, cell cycle regulation, DNA repair, and inflammatory responses. However, no clinically significant differences in gene expression were found between patients who received radiotherapy and those who did not. Tanic et al. identified differential expression of APOA1, MAP3K4, and MMP14 genes between tumors with and without NRT response. Mitogen-activated protein kinase kinase 4

(MAP3K4), a mitogen-activated protein kinase, was identified as a radiotherapy-specific biomarker for predicting survival in patients with adjuvant radiotherapy without distant metastasis. These findings suggest that MAP3K4 may serve as a biomarker for predicting preoperative and postoperative radiotherapy responses, as well as a potential target for combined radiotherapy-sensitizing therapy. This suggests the need for further preclinical studies and prospective clinical trials to validate these findings. The limitations of most studies lie in the selection of biomarkers not based on their radiotherapy specificity, predominantly relying on cell and animal models for foundational research, while clinical studies require large-scale long-term follow-up. This study also contributes to organoid development: Organoids are 3D cultured in vitro tissues that closely mimic cellular components, structural features, and functional properties of in vivo tissues. Widely used in both basic and translational research, they facilitate investigations into cancer onset, progression, tumor heterogeneity, gene-drug interactions, target prediction, and drug sensitivity testing. Compared with traditional 2D cell culture models, organoids exhibit complex spatial configurations simulating differentiated tissues, demonstrating interactions between cells and their surrounding matrix, as well as spatial positioning patterns. They also exhibit physiological responses similar to in vivo differentiated organs and maintain high similarity to their source tissues. These characteristics make organoids highly promising for both basic research and clinical applications. The resulting organoid disease models exhibit organ-specific structures and functions while replicating in vivo disease manifestations, effectively avoiding species-specific variations. Patient-derived tumor organoids (PDTOs) refer to models established through in vitro cultivation of patients' tumor tissues (typically malignant specimens obtained via surgical resection or biopsy), which closely resemble the patient's tumor type. Compared with other tumor models, PDTO (Patient-Derived Tumor Oligonuclear Organoids) largely preserves the histological and genetic information of original tumor tissues, maintaining structural similarity to the primary tumor. This makes it an excellent in vitro "surrogate" for patient tumors. Additionally, tumor organoids offer advantages such as ease of operation, minimal required tissue volume,

rapid model establishment, convenient in vitro observation, and stable genome stability. These features make them highly promising for disease modeling, clinical cancer research, and drug sensitivity testing. With moderate costs, short culture timelines, high success rates, and conversion rates, they are expected to provide a new cost-effective platform for drug screening and development. Furthermore, continuous monitoring of pre-and post-radiotherapy tumor biopsy specimens from patients with known clinical responses can help evaluate radiobiological characteristics, specific biomarkers/imaging markers, and optimal radiotherapy-drug combination regimens for breast tumors/normal tissues. This approach promotes more effective treatment selection, avoids overtreatment, and reduces associated medical expenses.^{4,30 – 32}

In imaging evaluation, conventional breast X-ray and two-dimensional grayscale ultrasound primarily assess neoadjuvant therapy efficacy based on tumor morphology and size changes. However, relying solely on morphological and dimensional measurements may fail to comprehensively evaluate neoadjuvant treatment outcomes, as some tumors may show minimal volume changes while exhibiting diminished or lost cellular activity. Compared to other breast imaging modalities, MRI demonstrates advantages in multi-parameter, multi-slice functional imaging capabilities. Its dynamic contrast enhancement, diffusion-weighted imaging (DWI), and magnetic resonance spectroscopy (MRS) allow comprehensive assessment of tumor morphology, hemodynamic changes, and functional metabolic alterations. Studies confirm that breast MRI shows high consistency with histopathological evaluation of neoadjuvant therapy efficacy in breast cancer, closely approximating the extent of pathological changes compared to histological findings. Additionally, MRI outperforms clinical palpation, X-ray, and ultrasound in distinguishing residual lesions from fibrosis and detecting microscopic residual lesions post-neoadjuvant therapy. As a standard imaging method, MRI has become the primary assessment tool for evaluating breast cancer's response to neoadjuvant therapy. Conventional breast MRI evaluation metrics include tumor morphology and size, time-signal intensity curve patterns after dynamic contrast enhancement, MRI semi-quantitative/quantitative parameters, ADC values from DWI, and cholinergic

peak variations from MRS. While non-invasive tumor prognosis assessment and predictive biomarkers hold significant advantages, their clinical validation and application progress remain slow. Preoperative treatment studies demonstrate advantages in validating imaging biomarkers, enabling correlation analysis between preoperative/interoperative imaging features and pathological/molecular endpoint indicators. Advances in imaging-based tumor biology capabilities could, in turn, facilitate research into adaptive radiotherapy using strategies such as dose-fine distribution, individualized dose and fractionation plans, and radiotherapy combined with drugs.^{4,33,34}

The evolving multidisciplinary management paradigm for breast cancer has driven our efforts to develop personalized treatment strategies and integrate various approaches. As a non-mainstream treatment modality, preoperative high-dose neoadjuvant radiotherapy (NART) has emerged as a novel therapeutic option for locally advanced luminal (HER2-) and triple-negative breast cancer patients who have demonstrated suboptimal response to neoadjuvant chemotherapy. This study aims to investigate the efficacy and safety of combining neoadjuvant chemotherapy with preoperative high-dose radiotherapy in locally advanced luminal (HER2-) and triple-negative breast cancer patients through a prospective Phase II single-arm trial.

2. Objective of the study

2.1 Research task: Prospective enrollment of eligible patients with locally advanced breast cancer, using intensity-modulated technology to implement preoperative large fraction of whole breast \pm chest wall + supraclavicular lymph node drainage area + axillary lymph node drainage area \pm internal mammary lymph node drainage area. Follow-up observation of radiation toxicity and efficacy.

2.2 Research objectives: To clarify the safety and feasibility of preoperative large fraction radiotherapy for patients with locally advanced breast cancer, and to provide a basis for future phase III clinical studies.

2.1 Objectives: Eligible patients with locally advanced breast cancer were prospectively enrolled. Imrt was used to perform preoperative hypofractionated whole breast irradiation \pm chest wall + supraclavicular lymph node irradiation+axillary lymph node irradiation \pm internal mammary lymph node irradiation. The toxicity and efficacy of radiotherapy were followed up.

3. Study endpoints

3.1 Primary study endpoint: pCR rate (pathological complete response rate)

3.2 Secondary study endpoints:

3.2.1 Early adverse reactions: acute skin injury, breast swelling and pain, local infection, radiation mucositis, radiation pneumonia, upper limb lymphedema rate, blood biochemical reaction and systemic reaction

3.2.2 Other adverse events:

Postoperative complication rate (delayed incision healing rate, secondary surgery rate), late adverse reaction rate (including late skin injury, breast swelling and pain, cosmetic effect, radiation cardiomyopathy, pulmonary fibrosis, radiation brachial plexus injury, upper limb lymphedema), quality of life (EORTC QLQ30, BR-23 questionnaire)

3.2.3 Efficacy indicators: local recurrence rate, regional recurrence rate, pathological response rate (according to Miller-Payne classification), npCR (near npCR) rate, RCB (residual tumor burden) rate, event-free survival, distant metastasis rate, tumor-free

survival rate, and overall survival rate

3.2.4 Transformation research indicators:

Tissue samples: including pre-adjuvant therapy and surgical specimens. Some are used for organoid construction; others are used for single-cell sequencing; paraffin tissue samples: some tissue blocks are fixed in centrifuge tubes containing formalin, which can be used for spatial transcriptome sequencing.

Peripheral blood samples: The plasma part can detect immune factors and ctDNA, and PBMC (peripheral blood mononuclear cells) can be enriched by flow or mass spectrometry, as well as T and NK. CTDNA is planned to collect 5-10 patients.

(1) Fecal Sample Collection Protocol: Collect stool samples at the following intervals: 1 week prior to radiotherapy, within 3 days after radiotherapy completion, 1 week before initial chemotherapy, 1 week before the 3rd and 5th chemotherapy cycles, 1 week preoperatively, and 1 week postoperatively. (Pre-collection instructions: Record the patient's oral antibiotic or probiotic intake history from 2 weeks prior to the designated collection time. Instruct patients to collect stool in a clean container (e.g., disposable toilet bowl), avoiding contamination from urine or toilet surfaces. Collect fresh mid-to-late portion stool using a sterile spoon inside the collection tube (1-3 scoops, 1g). Store samples in -80°C ° C freezer within 30 minutes after collection. Sample labeling: Tumor type code + medical record number + collection date. If possible, collect family members' samples as paired control specimens.)

(2) Saliva: Samples are collected one week before radiotherapy, within three days after radiotherapy completion, one week before the first chemotherapy session, one week before the 3rd and 5th chemotherapy cycles, and one week before surgery. (Pre-collection instructions: Record the patient's history of oral antibiotics, probiotics, and dental procedures (like fillings or extractions) two weeks prior to the designated time point. Ensure the patient rinses their mouth with 30ml of purified water for 30 seconds on the collection day, then empties it into the saliva sampling cup. Store samples in an -80 °C ° C freezer within 30 minutes after collection. Document detailed sampling times (Sample code: Tumor type code + Medical record number + Collection time). If possible, collect family members as paired control samples.)

(3) Imaging: Breast MR was performed 2 weeks before radiotherapy, 1 week before the first chemotherapy, 1 week before the 3rd and 5th cycle of chemotherapy, and 1 week before surgery

(4) Imaging: Breast MR was performed 2 weeks before radiotherapy, 1 week before the first chemotherapy, 1 week before the 3rd and 5th cycle of chemotherapy, and 1 week before surgery

(5) Imaging part: MRI of breast was performed 2 weeks before radiotherapy, 1 week before the first chemotherapy, 1 week before the third and fifth cycles of chemotherapy, and 1 week before surgery

4. Enrollment screening criteria

Entry criteria

Women aged 18 to 70

- 1) The pathological diagnosis was invasive breast cancer
- 2) cT3-4, cN1-2, M0 (AJCC Cancer Staging Manual, 8th edition), molecular subtype was luminal (HER2-) and triple-negative, and the primary lesion volume was reduced by less than 50% after 2 cycles of neoadjuvant chemotherapy
- 3) Generally in good condition (KPS>70 points), organ function is tolerable, and no severe complications of poor control
- 4) Generally in good condition (KPS>70 points), organ function is tolerable, and no severe complications of poor control
- 5) MRI scans are acceptable
- 6) Be eligible for follow-up
- 7) Sign the informed consent form

Exclusion criteria

- 1) gestation period
- 2) Simultaneous bilateral breast cancer
- 3) History of chest radiotherapy
- 4) There is active connective tissue disease
- 5) Inflammatory breast cancer

- 6) Breast size is large ($>600\text{ml}$) and $\text{BMI} > 30$
- 7) diabetes mellitus
- 8) The upper and lower regions of the clavicle and the internal mammary region showed positive lymph nodes
- 9) Use of immunotherapy drugs such as PD-1/PD-L1
- 10) History of other malignancies, excluding but not limited to curable early papillary thyroid carcinoma, non-malignant melanoma skin cancer, cervical carcinoma in situ, contralateral breast carcinoma in situ, early lung cancer, etc

Standards for shedding

- 1) Significant tumor progression during radiotherapy or systemic therapy
- 2) Serious non-oncological disease that makes continued treatment or routine follow-up impossible
- 3) The patient volunteered to withdraw

Baseline check, Table 1

Pre-entry screening (mandatory)		testing time
History and physical examination	General condition score, height, weight	Within 1 week prior to treatment
Pathological review	Postoperative pathological sections from the external hospital (lower level hospital) need to be reviewed again by the research unit, including relevant immunohistochemistry	Pre-treatment preparations
routine blood test	Absolute white blood cell, lymphocyte and neutrophil count, hemoglobin, platelets	
Liver and kidney function	AST, ALT, total bilirubin, creatinine	Within 1 week prior to treatment
blood fat	Triglycerides (TG), total cholesterol (TC), low density lipoprotein cholesterol (LDL-C)	
myocardial enzyme	CK-MB, TNI, NT-proBNP	

iconography	
Breast X-ray/ breast B-ultrasound + breast MRI;
 
Chest enhanced CT (preferably thin layer) in our hospital;
 
B-ultrasound of bilateral axilla, neck, supraclavicular and inner breast;
 
Liver ultrasound/or enhanced CT/or MRI;
 
brain MR;
 
Whole-body bone scan
 
Whole-body PETCT (optional)
	Within 2 weeks (maximum 4 weeks) prior to whole body treatment
Toxicological evaluation	Baseline toxicity assessment, photos (beauty evaluation), and written records	1 week before radiotherapy
Table of breast beauty effect and quality of life	BREAST-Q questionnaire	
Thyroid examination	T3, T4, FT3, FT4, TSH; thyroid ultrasound	Within 1 month before treatment, after every 2 cycles of chemotherapy,
cardio-pulmonary function	Twelve lead electrocardiogram	preoperatively, and 3 months, 6 months, and 1 year after surgery
	echocardiogram	
	lung function	Two weeks before surgery (maximum 1 month)
Organizational specimens, blood specimens, urine and stool specimens	Fine needle aspiration tissue and surgical specimens before radiotherapy	
	Blood specimens and urine specimens were collected within 2 weeks before radiotherapy, on the day of radiotherapy end, before the first, third and fifth cycles of chemotherapy, preoperatively, postoperatively, 3 months after surgery and 1 year after surgery	

5. Experimental design and statistical processing

5.1. Sample size

This exploratory study investigates the design and optimization of neoadjuvant chemotherapy combined with preoperative medium-dose fractionated radiotherapy (MFRT) in breast cancer. The prospective single-arm Phase II clinical trial aims to compare pathological complete response rates (PBR) and acute-phase adverse event (AEE) rates between this regimen and standard treatment protocols. Specifically, it evaluates the efficacy of preoperative MFRT in locally advanced luminal HER2-negative triple-negative breast cancer patients. Given the exploratory nature of the study and limited prior research on preoperative MFRT, a total sample size of 50 cases was determined to ensure robust analysis.

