Imaging studies: analysis of breast ultrasound and breast MR imaging parameters before and after treatment.

Follow-up time: 5 years

Statistical methods: Based on the principle of intention processing analysis, pCR rate and incidence of adverse reactions were calculated. Kaplan-Meier was used to calculate local recurrence rate, regional recurrence rate, distant metastasis rate, tumor-free survival rate and total survival rate.

technology roadmap :

2 cycles of neoadjuvant chemotherapy followed by reduction of primary lesion volume less than 50% + 3 weeks of neoadjuvant radiotherapy + 4 cycles of neoadjuvant chemotherapy + surgery ± adjuvant therapy

1. Research Background

Breast cancer (BC) is the leading malignancy among women globally, ranking first in cancer-related deaths and fifth in overall cancer mortality. In 2020, it surpassed lung cancer to become the world's most common malignancy. China accounts for 416,000 new cases annually, making it the primary cause of cancer-related deaths among women and representing 18.4% of the global breast

cancer burden.1 Non-metastatic locally advanced breast cancer (LABC) patients in China account for about 12-15%, significantly higher than that in the United States and Europe (about 8.5% in the United States and 4% in Europe). Due to its lower overall survival rate, higher recurrence rate, and risk of distant metastasis, Localized Axillary Breast Cancer (LABC) significantly impacts the overall efficacy and survival of breast cancer patients. The current treatment model for LABC patients remains a major clinical challenge. In clinical practice, these patients typically undergo primary systemic therapy (PST) to achieve tumor downstaging before surgery, followed by adjuvant treatments (primarily radiotherapy and medication). Radiotherapy serves as a crucial therapeutic approach to reduce local recurrence rates and improve overall survival rates.

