Preoperative neoadjuvant radiotherapy (NART) is a common treatment option for many tumors (such as esophageal carcinoma, rectal carcinoma, soft tissue sarcoma, etc.). By bringing radiotherapy and systemic chemotherapy to the preoperative stage to strengthen preoperative treatment, reduce the stage and eliminate micro-metastatic lesions early to improve overall survival.3. In breast cancer patients, NART has the opportunity to further shrink the tumor, improve the probability of breast preservation, and may not need to perform axillary lymph node dissection, allowing axillary surgery downgrading.4 Many studies have found that patients with pCR after neoadjuvant therapy (NAT) generally have a better prognosis than non-pCR, and NART is also one of the treatment options to reduce the stage. But this combination has not yet been widely used in breast cancer patients.

In all breast cancers, luminal breast cancer accounts for 50-70% (LuminalA type about 30-40%, LuminalB type about 20-30%), among which HR+HER2-type breast cancer patients have poor efficacy of neoadjuvant chemotherapy, with objective response rate (ORR) about 40-60%, partial response rate (PR) about 30-50%, and complete response rate (CR) usually not more than 15%. When neoadjuvant chemotherapy shows poor efficacy, these patients typically opt for direct surgical

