5.2 Statistical analysis

- 1) Kaplan-Meier statistical analysis was used for survival analysis, log-rank test was used to compare survival curves, and Pearson's chi-square test was used to compare categorical variables. When the p value was less than 0.05, the difference was considered statistically significant.

6. Radiation therapy

Prior to initiating treatment, the primary tumor site should be marked with photographic documentation for subsequent resection. The primary lesion may be identified using tattoos, superficial projections, or metallic markers. These metallic markers can be placed at the tumor center and/or margins. When no intramammary markings are available, external identifiers such as superficial tattoos, mass projections, or diagrams may be employed. Clinical examinations combined with ultrasound imaging should thoroughly evaluate axillary lymph nodes. If ultrasound suggests suspicious axillary lymph nodes during baseline assessment, a guided ultrasound-assisted biopsy should be performed to determine the status of these lymph nodes.

Photography (front, left oblique, right oblique): 1 week before radiotherapy, the day

of radiotherapy end, 1 week before surgery, 1 month after surgery

Radiotherapy: CT positioning is used to delineate the target area and normal tissue for dose assessment.

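### Section 5.1 gives a single-arm trial a comparative aim with no comparator, reference rate or threshold, and calls 50 patients robust without stating any precision

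*Protocol*

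**What the plan says.** Protocol Section 5.1 (Sample size) describes a prospective single-arm phase II trial that "aims to compare pathological complete response rates (PBR) and acute-phase adverse event (AEE) rates between this regimen and standard treatment protocols". Its next sentence speaks only of evaluating efficacy. The section gives this reason for the number of patients: "Given the exploratory nature of the study and limited prior research on preoperative MFRT". It then concludes that "a total sample size of 50 cases was determined to ensure robust analysis".

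The rest of the protocol is not comparative for these rates:

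- The Research overview states the objective as evaluating efficacy and safety. Under Statistical methods it says that "pCR rate and incidence of adverse reactions were calculated".
- The end of Section 1 describes investigating efficacy and safety "through a prospective Phase II single-arm trial".
- Section 2.2 concerns safety and feasibility.
- Section 3.1 names the pCR rate as the primary endpoint, with no reference value.
- Section 5.2 says that Pearson's "chi-square test was used to compare categorical variables", with p below 0.05 as the significance rule. It names no groups and does not state sidedness.

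Section 1 contains two background response figures. For HR+/HER2- disease it gives a "complete response rate (CR) usually not more than 15" per cent, and for conventional neoadjuvant regimens a pCR rate of about 35%. Neither is carried into Section 5.

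**The concern.** A single arm can be compared with standard treatment only through an external cohort or a fixed reference rate, and the protocol adopts neither. The chi-square test in 5.2 cannot fill the gap, because it needs a second group and none is named.

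The primary endpoint is involved. If no reference is fixed in advance, how the pCR rate reads against standard treatment depends on which outside figure is later set beside it. The same holds for acute adverse events, for which no standard-treatment rate is adopted.

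The claim of robustness has a similar weakness. An exploratory setting and little prior research are reasons to accept a pragmatic size. They do not show that the analysis will be robust, and a reader of 5.1 cannot tell how wide the uncertainty will be.

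**Working it through.** **1. Can the plan's own figure be reproduced?** No. A sample size of 50 would follow from a null rate, a target rate, an error level and power, or from a target interval width. Section 5.1 gives none of these. The 0.05 in 5.2 is a general cut-off that is not tied to a pCR hypothesis or to the number 50.

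**2. What precision do 50 patients give?** This needs only n = 50 (Section 5.1); the event counts x are illustrative. The exact (Clopper-Pearson) 95% limits are

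lower = Beta quantile 0.025 with parameters (x, n − x + 1); upper = Beta quantile 0.975 with parameters (x + 1, n − x).

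| Events out of 50 | Rate | Exact 95% interval |
|---|---|---|
| 0 | 0% | 0 to 7.1% |
| 5 | 10% | 3.3 to 21.8% |
| 10 | 20% | 10.0 to 33.7% |
| 20 | 40% | 26.4 to 54.8% |
| 25 | 50% | 35.5 to 64.5% |

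For zero events the upper limit is 1 − 0.025^(1/50) = 0.0711. The interval is widest at 25/50: 64.47 − 35.53 = 28.9 percentage points.

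**3. Would the choice of reference matter?** As an illustration, take the two Section 1 figures, 15% and 35%, as if each were the reference rate p0. The protocol does not adopt them. The 15% is a complete response rate, not called pCR, and is given as an upper bound. The 35% is not clearly tied to a subtype. Neither describes the enrolled patients, who under entry criterion 2 (Section 4) have shrunk by less than 50% after two cycles and come from two subtypes with no fixed mix.

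Use one error level throughout: one-sided 2.5%, which matches a two-sided 95% interval. This level is my choice, since 5.2 states no sidedness. The cut-off is the smallest r for which P(X ≥ r | n = 50, p0) is at most 0.025.

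- p0 = 15%: P(X ≥ 13) = 0.0301 and P(X ≥ 14) = 0.0132, so at least 14/50 is needed. The intervals agree: 13/50 has a lower limit of 14.6% and 14/50 one of 16.2%.
- p0 = 35%: P(X ≥ 24) = 0.0396 and P(X ≥ 25) = 0.0207, so at least 25/50 is needed. The intervals agree: 24/50 has a lower limit of 33.7% and 25/50 one of 35.5%.

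So any result from 14 to 24 pCRs (14/50 = 28% to 24/50 = 48%) would exceed one figure and not the other.

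**The case against.** The strongest reply is that the comparative aim is a single sentence. The objectives, the primary endpoint and the synopsis all describe evaluating and calculating rates, and the sentence after it in 5.1 does too. On this view estimation is already the working plan, and the sentence is loose or poorly translated; it abbreviates pathological complete response as PBR. This stands as a limit on the point: the defect is one contradictory aim plus an unsupported claim of robustness, not a trial built on a comparison. It does not remove the point. The sentence names both outcomes and the kind of comparator, and 5.2 supplies a significance rule for differences.

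A second reply is that exploratory phase II trials may be sized pragmatically. That is accepted. A reader might infer that 50 is too few, but the documents do not support this, because no target is stated against which 50 could fail.

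A third reply is that a statistical analysis plan may hold the interval method, a benchmark or the groups for the chi-square test. Their absence from the protocol is not counted here. The aim and the sample-size rationale, however, are fixed in Section 5.1 itself.

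Finally, a reader might infer that a phase III decision hangs on the missing pCR threshold, since Section 2.2 says that the trial is "to provide a basis for future phase III clinical studies". That sentence ties the basis to safety and feasibility, and no go/no-go rule on pCR is stated. The phase III argument is therefore not made.

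**Conclusion.** The point holds as a contradiction within the protocol. Section 5.1 promises a comparison that the single-arm design and the stated analysis do not provide, and it claims robustness without a precision or operating figure. Estimating a single-arm pCR rate is valid and is not criticised.

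The precision results rest only on n = 50, all 50 being evaluable, and exact binomial limits. The cut-offs of 14 and 25 rest on borrowed background figures and an assumed one-sided 2.5% level. They show only that the choice of reference matters; they do not say what the reference should be. This should be fixed, but it does not threaten the validity of the trial.

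**What to change.** In Section 5.1, replace the comparative aim and the claim of robustness with wording such as:

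> This exploratory single-arm trial estimates the pCR rate and acute adverse event rates with exact 95% confidence intervals; no formal comparison with standard treatment is made. With 50 patients, 10 pCRs would give 20% (95% CI 10.0–33.7%), the interval is at most 28.9 points wide, and no event of a given type would still allow a rate up to 7.1%.

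If a statement against standard treatment is kept, fix a justified reference rate before results are known. It should suit the subtype mix and patients with a poor early response. Use an exact one-sample test against it with stated sidedness, and do the same for any adverse event rate to be compared.

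The first route costs two sentences, with no extra patients, visits or data; its downside is a more modest claim. The second route needs a reference rate for early poor responders, which this protocol does not contain.
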